9.2. Sample Size Considerations

[figure not shown]
9.2.1. Sample Size Assumptions

The study is not powered to detect pre-defined differences. Initially, approximately 70 subjects will be recruited.

Following interim analysis the number of subjects in some or all treatment arms may be increased following sample size re-estimation, up to a maximum of 120 total subjects in the study where up to a maximum of 25, 45, 30 and 20 will be randomized to placebo, belimumab monotherapy, co-administration therapy and rituximab monotherapy, respectively. This will be dependent on variability and placebo rates for certain parameters. More details will be included in the RAP.

The primary objective of the study is safety, where a number of safety events are of interest. Using a Bayesian approach to determine the confidence interval around an observed safety event in the co-administration group, we would have a flat Beta(1,1)

prior, and if we were to observe 1 safety event in 20 then the posterior distribution would be Beta (2,20), as outlined below:

We can be 95% certain that the true probability of the safety event lies between 0.01 and 0.24.

For supportive information, with 20 patients randomized to belimumab or the belimumab / rituximab arm and 10 to placebo, the smallest difference in ESSDAI between the two treatment groups that would be statistically significant would be -3.30, assuming a placebo change from baseline of -1.7 [TEARS, [Devauchelle-Pensec](#), 2014], a standard deviation of 4.192 [BELISS, [Mariette](#), 2015] and alpha=5%.

Following the interim analysis, if the number of subjects were to increase to those outlined above then the following would apply for the continuous ESSDAI score, assuming a placebo change from baseline of -1.7 [TEARS, [Devauchelle-Pensec](#), 2014], a standard deviation of 4.192 [BELISS, [Mariette](#), 2015] and alpha=5%:

Placebo	Active	Difference	Placebo N	Active N	Power to detect difference
-1.7	-4.7	3	25	45	82%
-1.7	-4.7	3	25	40	80%
-1.7	-4.7	3	25	35	78%
-1.7	-4.7	3	25	30	75%

For responder endpoints, including the proportion of patients who achieve a 30% improvement in oral dryness response scale; or the proportion of patients who achieve a 30% improvement in stimulated salivary flow, then the smallest difference between the 2 treatment groups that would be statistically significant is 33%, assuming a placebo response of 14%, for example.

Twenty subjects randomized to the rituximab arm, would enable a reasonable evaluation of the impact of treatment on the underlying immunological mechanisms but not the clinical efficacy.

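### Is the 33-point smallest significant responder difference in Section 9.2.1 wrong, given that no arm sizes, alpha or test stand beside it?

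*Protocol*

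**What the plan says.** All the figures are in Protocol Section 9.2.1. That section opens by saying that "The study is not powered to detect pre-defined differences". It later offers, as supportive information, the smallest significant ESSDAI difference "with 20 patients randomized to belimumab or the belimumab / rituximab arm and 10 to placebo", at an alpha of 5%. It then turns to the enlarged design: "if the number of subjects were to increase to those outlined above then the following would apply for the continuous ESSDAI score". The table that follows gives power for 25 placebo patients against 30 to 45 on active treatment.

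After the table comes one sentence on responder endpoints, such as "the proportion of patients who achieve a 30% improvement in oral dryness response scale" and the same improvement in stimulated salivary flow. It says that "the smallest difference between the 2 treatment groups that would be statistically significant is 33%, assuming a placebo response of 14" per cent, and marks this as an example. It does not repeat arm sizes, alpha or sidedness, and it names no test.

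**The concern.** The two ESSDAI statements before it give arm sizes, standard deviation and alpha. The responder sentence gives only a placebo rate, so a reader must guess which design it describes.

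If it belongs with the table it follows, 33 points is far above the significance threshold. If it belongs with the initial 20 v 10 design, the most familiar test (pooled chi-square) does not reach significance at 14% v 47%. Either way the number seems not to fit. It is also the only sensitivity figure the protocol gives for the two dryness responder endpoints. If it were too small, the comparison with 10 placebo patients would look more sensitive than it is.

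**Working it through.** **Inputs.** From Section 9.2.1: placebo rate 0.14; stated difference 0.33, so active rate 0.47; 10 placebo v 20 active initially; 25 placebo v 30 to 45 active if enlarged; alpha 5% (stated for ESSDAI). Two-sided testing is my assumption.

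**Reproducing 33 at 20 v 10.** Solve d = t × SE(d), with unpooled n-1 variances and t(28) = 2.048:

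SE(d) = √[0.14 × 0.86 / 9 + (0.14 + d)(0.86 − d) / 19]

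The solution is d = 0.333: SE = 0.1628, and 2.048 × 0.1628 = 0.333. This rounds to the stated 33.

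**Other approximations at 20 v 10, two-sided 5%, placebo 14%:**

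| Method | Threshold (points) |
|---|---|
| Unpooled z | 30.6 |
| Unpooled t(28) | 32.0 |
| Unpooled t(28), n-1 variances | 33.3 |
| Welch | 33.6 |
| Arcsine | 33.8 |
| Likelihood ratio | 35.1 |
| Pooled chi-square | 37.0 |
| Continuity-corrected chi-square | 45.2 |

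**Chi-square at exactly 14% v 47%.** The pooled rate is (10 × 0.14 + 20 × 0.47)/30 = 0.36. SE = √[0.36 × 0.64 × (1/10 + 1/20)] = 0.186, so z = 0.33/0.186 = 1.78 and p = 0.076: not significant by this test.

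**Whole patients.** At 20 v 10, differences move in steps of 5 points, so any such threshold is nominal.

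| Placebo responders | Unpooled t(28) | Unpooled t(28), n-1 | Chi-square | Fisher |
|---|---|---|---|---|
| 1/10 | 30 (8/20, p = 0.048) | 35 (9/20, p = 0.029) | 40 (10/20, p = 0.032) | 40 (10/20, p = 0.0485) |
| 2/10 | 35 (11/20, p = 0.047) | 40 (12/20, p = 0.030) | 40 (12/20, p = 0.038) | 50 (14/20, p = 0.019) |

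The answer runs from 30 to 50 points according to the test and the placebo count, and 33 lies inside that span.

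**Enlarged sizes, pooled chi-square.** 23.5 (25 v 30), 22.9 (25 v 35), 22.4 (25 v 40), 22.0 (25 v 45). A 33-point difference gives p = 0.009 at 25 v 30 and p = 0.006 at 25 v 45. Every two-sided 5% form tried at these sizes falls between 19 and 28, so 33 cannot be the threshold there.

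**Which design is meant.** The sentence that introduces the table confines it to the continuous ESSDAI score. The responder sentence uses the construction of the 20 v 10 paragraph: the smallest observed difference that reaches significance, not the power to detect one. The number fits 20 v 10 under a usual approximation and fits no enlarged size. Wording and arithmetic both point to 20 v 10.

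**The case for a change.** The strongest reply is that the methods giving about 33 behave poorly with 10 placebo patients. If both arms truly respond at 14%, enumerating every 10 v 20 table gives a two-sided rejection rate of 7.8% for the n-1 t(28) rule and about 15% for arcsine, against 3.4% for chi-square. On that view a threshold taken from those rules is optimistic whoever computed it, and the protocol should have used a safer test.

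Those rates are right, but they come almost wholly from tables in which one arm has no responders. Counting only tables with at least one responder in each arm, the rejection probabilities are 0.9%, 1.0% and 1.0%. Outcomes near 14% v 47% are not where the methods part company on error rate. The argument is a reason to prefer chi-square or Fisher for an actual analysis; it does not show that a planning approximation was miscalculated. Choosing a responder test, if one is used, is properly left to the analysis plan. Section 9.4.3 itself analyses oral dryness and salivary flow as continuous changes by mixed model.

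Two things stand. The sentence should ideally have carried its arm sizes, sidedness and test. And 33 is at the favourable end: a reader who expects chi-square or Fisher should think of 37 points, or 40 and more on attainable counts.

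**Conclusion.** No change is needed. Read at 20 v 10 with two-sided 5%, the stated 33 agrees with an ordinary unpooled t calculation (33.3) and is about 4 points below the chi-square threshold (37.0 − 33 = 4.0). That gap reflects a choice of method, not a demonstrated mistake. The apparent conflict with the table's sizes disappears once the table is read as the protocol introduces it, for ESSDAI only.

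Nothing rests on the number. The study is declared unpowered, the sentence is offered as an example, and Section 9.1 calls the efficacy comparisons exploratory. Section 3 lists oral dryness and salivary flow as scores over time with no responder endpoint, and Section 9.2.3 ties re-estimation to ESSDAI. Supplying the missing labels would tidy the text without altering a sample size, an analysis or a conclusion.

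This rests on two assumptions that the document does not state outright: that the sentence refers to 20 v 10, and that alpha is two-sided 5%. If the enlarged sizes had been meant, 33 would be wrong as a threshold (about 22 to 24 by chi-square). It would then overstate the difference needed, and still nothing in the plan would depend on it.

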9.2.2. Sample Size Sensitivity

A sample size sensitivity analysis has been conducted on the primary endpoint, to investigate different safety event rates. If the number of subjects who completed the 24 weeks is lower than 20 in the co-administration group, then the true incidence rates of safety events that could not be ruled out (as outlined in Section 9.2.1) would change. These changes are outlined in the table below:

N completing study	Number of particular safety events observed with co-administration	Upper limit of exact 95% CI indicating that a true incidence rate of x% could not be ruled out
18	0 / 18	18%
18	1 / 18	26%
16	0 / 16	20%
16	1 / 16	29%
14	0 / 14	22%
14	1 / 14	32%

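### Are the six upper limits in the Section 9.2.2 safety table wrong because the column calls them exact 95% limits?

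*Protocol*

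**What the plan says.** Section 9.2.1 (Sample Size Assumptions) sets out how the precision of a safety event rate is judged: "Using a Bayesian approach to determine the confidence interval around an observed safety event", with a flat Beta(1,1) prior. Its worked example is 1 event in 20 subjects, giving a Beta(2,20) posterior and the statement "We can be 95% certain that the true probability of the safety event lies between 0.01 and 0.24".

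Section 9.2.2 (Sample Size Sensitivity) asks what happens with fewer than 20 completers on co-administration. It says that "the true incidence rates of safety events that could not be ruled out (as outlined in Section 9.2.1) would change", then gives a table whose last column is headed "Upper limit of exact 95% CI indicating that a true incidence rate of x% could not be ruled out". The entries are 18% (0/18), 26% (1/18), 20% (0/16), 29% (1/16), 22% (0/14) and 32% (1/14).

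**The concern.** The header and the method do not match. A statistician who sees an exact 95% CI for a binomial proportion will use Clopper-Pearson and will fail to reproduce any row. Every printed limit is below its Clopper-Pearson counterpart, which is the more reassuring direction for safety.

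Safety is the primary objective and is not formally tested (Sections 9.1 and 9.4.2). Together with the 1/20 example, this table is therefore the protocol's main numerical statement of what the co-administration arm can rule out. If the figures were miscalculated, the protocol would overstate its ability to exclude a harmful event rate. If only the label were wrong, a reader of the header alone could miss that the limits depend on a prior.

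**Working it through.** **Inputs.** The prior Beta(1,1), the 1/20 example and its interval come from Section 9.2.1. The six pairs of events x and completers n, and the six printed limits, come from Section 9.2.2.

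**Step 1: reproduce the 9.2.1 example.** The posterior is Beta(1+x, 1+n−x). For 1/20 this is Beta(2,20), whose 2.5% and 97.5% points are 0.0117 and 0.2382. The protocol prints 0.01 and 0.24, so the interval is the equal-tailed one.

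**Step 2: apply the same method to the table.** The upper limit is the 97.5% point of Beta(1+x, 1+n−x). With no events this has the closed form 1 − 0.025^(1/(n+1)). For 0/18 that is 1 − 0.025^(1/19) = 17.65%.

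**Step 3: take the header literally.** The two-sided Clopper-Pearson upper limit is the 97.5% point of Beta(x+1, n−x). With no events this is 1 − 0.025^(1/n). For 0/18 that is 1 − 0.025^(1/18) = 18.53%.

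| Events / n | Printed | Flat-prior limit | Clopper-Pearson limit (rounded) |
|---|---|---|---|
| 0/18 | 18% | 17.65% | 18.53% (19%) |
| 1/18 | 26% | 26.03% | 27.29% (27%) |
| 0/16 | 20% | 19.51% | 20.59% (21%) |
| 1/16 | 29% | 28.69% | 30.23% (30%) |
| 0/14 | 22% | 21.80% | 23.16% (23%) |
| 1/14 | 32% | 31.95% | 33.87% (34%) |

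The flat-prior limits round to all six printed values; Clopper-Pearson rounds to none. Truncating Clopper-Pearson instead of rounding would recover only 0/18 and 0/16. One-sided Clopper-Pearson, Jeffreys, Wilson, Agresti-Coull, mid-P and highest-posterior-density limits were also tried, and none reproduces the whole column.

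**Step 4: size of the mismatch.** The unrounded gap runs from 0.88 points (0/18) to 1.92 points (1/14). The two formulas differ only in the second Beta parameter, n−x+1 against n−x. The flat-prior limit for x/n is therefore the Clopper-Pearson limit for x/(n+1), so the gap is worth one extra event-free subject. Put another way, the binomial probability of x or fewer events at the printed rates is 0.028, 0.032, 0.028, 0.031, 0.031 and 0.034, against a nominal 0.025. Read as Clopper-Pearson limits, the printed values would carry two-sided confidence between 1 − 2×0.034 = 93.2% and 1 − 2×0.028 = 94.4%.

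**Step 5: does anything use the table?** The study stopping criteria in Section 5.4.4 use event counts among the first five co-administration subjects and then an observed rate above 20%. Sample size re-estimation in Section 9.2.3 depends on ESSDAI variability and placebo means. Section 9.4.2 excludes formal testing of safety data. Section 9.2.1 says the study is not powered for pre-defined differences. None of these takes a limit from the table.

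**The case for a change.** The best argument for acting is that the label and the figures both stand in the protocol, so this is a misstatement and not a detail left to the analysis plan. *Exact CI* is an established frequentist term, and reading it as computed exactly from the posterior is strained. Section 9.2.1 adds to the confusion by calling its own Bayesian result a confidence interval. All six discrepancies run in the reassuring direction, on the primary endpoint, and correcting a header costs nothing.

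Part of this stands. *Exact* is the wrong word, and *credible* would be better than *confidence* in both sections. What does not stand is the claim that the reader is misled about the method. The sentence above the table points back to Section 9.2.1, the subsection immediately before, which states the Bayesian approach, the prior, the posterior and an interval computed in the same way. Only someone who reads the header without the sentence introducing it would miss the prior. Replacing the values with Clopper-Pearson limits would be a step back, because it would discard figures that are right on the stated method and would mean restating the 1/20 interval as well.

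**Conclusion.** The concern is right about one word and does not reach the plan. All six limits are correctly computed under the method Section 9.2.1 declares; the header misnames them. The largest consequence of a literal reading is 2 percentage points after rounding, in illustrative scenarios where the upper limit is already between 18% and 32%. That would not alter anyone's view of what 14 to 18 subjects can exclude. Relabelling would leave every value, the sample size and every decision rule as they are, so this is a clerical slip with nothing to gain from a change to the plan.

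The conclusion assumes that *exact* was meant in its usual Clopper-Pearson sense, and that no document outside the protocol, such as the safety review committee charter, takes these limits as thresholds. The protocol gives no sign that one does.

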9.2.3. Sample Size Re-estimation

At the interim analysis, the sample size may be re-estimated based on the emerging data from the study. The sample size may need to be re-estimated if higher variability or differing placebo means are observed for the ESSDAI, a key secondary endpoint. Therefore, any significant deviation from the assumptions used to design the study may result in changes to the number of subjects to be randomized. Further details will be included in the RAP and guidance document for interim decision making. A maximum of 120 subjects will be recruited into the study.

9.3. Data Analysis Considerations

9.3.1. Analysis Populations

Safety Population: The ‘Safety Population’ is defined as subjects who receive at least one dose of study medication. This population is used for the summary of all data including safety efficacy and pharmacodynamic (PD) data but excluding PK data.

Pharmacokinetic Population: The ‘PK Population’ is defined as subjects in the ‘Safety’ population who received an active dose and for whom a pharmacokinetic sample was obtained and analyzed. This population is used for the summary of PK data only. In the case of PK/PD, the Safety Population is used so that subjects receiving placebo can be included.

9.3.2. Interim Analysis

In line with routine pharmacovigilance, subjects’ blinded safety data will be reviewed on an ongoing basis during the study conduct by an internal GSK Safety Review Team (SRT).

An internal GSK Safety Review Committee (iSRC), independent of the study team, will maintain governance of the study and will periodically review all available data in an un-blinded manner with a focus on key safety parameters. A Therapeutic Area (Immuno-Inflammation) Data Assessment Committee (TA DAC), independent of the study team, will periodically review un-blinded efficacy data and at the interim analysis will advise the iSRC on adaptive design changes should such changes be required. An iSRC charter details the activities of these committees, including when and which data will be reviewed, how the integrity of the study will be maintained, and the membership of both committees. Once half of the planned subjects (i.e.: approximately 35 subjects) have completed their Week 24 assessments, a formal interim analysis will take place.

Appropriate available safety and efficacy data will be included in the interim analysis. The main purpose of the interim analysis is to assess the safety and tolerability of the study drugs. In addition, on an exploratory basis, preliminary efficacy analysis may be conducted to enable a sample size re-estimation and obtain an initial estimate of the effect size of the co-administration therapy and belimumab monotherapy. Following the interim analysis, a number of actions could be mandated by the iSRC: the study may continue as planned; one or more treatment arms may be dropped; the number of subjects in some or all treatment arms may be increased following sample size re-estimation, up to a maximum of 120 subjects in the study.

9.4. Key Elements of Analysis Plan

9.4.1. Primary Analysis and Follow Up Analysis

In addition to the interim analysis, there will be additional analyses for this study, corresponding to the primary analysis and the follow-up analyses. The primary analysis will occur after the data through the Week 52 visit (or withdrawal visit for those subjects who withdraw during double-blind treatment) for all subjects has been collected, verified and validated. The follow up analyses will occur after data through the 16-week generalized follow-up period and IFU periods for all subjects has been collected, verified and validated. All subjects and study site personnel (except the unblinded site pharmacist) will remain blinded until the follow up analyses have been completed.

9.4.2. Analysis of Primary Endpoints

No formal statistical testing will be performed on safety data.

All safety evaluations will be based on the safety population. Clinical interpretation will be based upon review and displays of AEs, laboratory values and vital signs. The principle consideration in this evaluation will be the investigator-reported relationships of either AEs or laboratory abnormalities to IP.

Safety data will be presented in tabular and/or graphical format.

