3. OBJECTIVES AND ENDPOINTS

Objectives	Endpoints
Primary	

 Safety and tolerability of anti-BLyS / anti-CD 20 co-administration therapy and anti-BLyS and anti-CD 20 monotherapies 	
 Safety and tolerability; including incidence of SAEs and AESIs.
Secondary	

 Clinical efficacy of anti-BLyS / anti-CD 20 co-administration therapy and anti-BLyS and anti-CD 20 monotherapies Assessment of anti-BLyS / anti-CD 20 co-administration therapy and anti-BLyS and anti-CD 20 monotherapies on tissue B-cells. 	
 ESSDAI score over time Stimulated salivary flow over time Oral dryness numeric response scale over time B cell quantification within salivary gland biopsy at Week 24

Objectives	Endpoints
Exploratory 
 Assessment of mechanism and durability of effect of anti-BLyS/anti-CD 20 co-administration therapy and anti-BLyS and anti-CD20 monotherapies. 	
 Ocular dryness numeric response scale over time Lacrimal gland function as measured by Schirmer's test. Physician's Global Assessment (PGA) of disease activity over time Serologic markers over time Change in peripheral blood leukocytes including B cell subsets over time BLyS levels in blood Immunogenicity of rituximab and belimumab Pharmacokinetics of rituximab and belimumab Change from baseline in the cellular composition of the salivary gland Sustained efficacy of anti-BLyS/anti-CD 20 co-administration at Week 52 Additional exploratory biomarkers may be evaluated 
 Transcriptomic analysis of blood and salivary gland B and T cell receptor clonal analysis in peripheral blood and salivary gland Proteomic assessment of the saliva
Health Outcomes 
 Gather preliminary information on patient reported outcomes of anti-BLyS/anti-CD 20 co-administration therapy and anti-BLyS and anti-CD 20 monotherapies 	
 ESSPRI score (and individual scale subscores) over time Fatigue and Discomfort- SICCA Symptom Inventory (PROFAD SSI SF) over time Patient Global Assessment (PtGA) of disease activity over time Subject exit interviews

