5.4.4. Study Stopping Criteria

The un-blinded iSRC will review the safety data on a regular basis. The study would be stopped if 2 of the first 5 co-administration therapy (belimumab + rituximab) subjects to complete Week 10 have IgG $<400 \text{ mg/dL}$ (confirmed by repeat test 1 week (>2 days) after the initial result) that is associated with a serious infection or if there are 2 fatal infections. After this point, the un-blinded iSRC will stop the study if the rate of IgG $<400 \text{ mg/dL}$ associated with serious infection or fatal infection rate exceeds 20% in the co-administration therapy arm.

[figure not shown]

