7.4.1.4. Adverse Events of Special Interest

A number of adverse events of special interest have been identified as part of the risk assessment outlined in Section 4.7.1 due to the co-administration of two biologics and will be monitored for the duration of the study. These AESIs include infections (including opportunistic), systemic infusion / injection reactions, hypersensitivity reactions, malignancy, psychiatric events (including suicidality), severe skin reactions (including Toxic Epidermal Necrolysis and Stevens-Johnson syndrome), immunogenicity, cardiac disorders, posterior reversible encephalopathy syndrome (PRES), PML, and AE's related to the biopsy procedure. The analyses of these events will be described in the Reporting and Analysis Plan.

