10.8. Review Committees

10.8.1. Internal Safety Review Committee (iSRC) and Therapeutic Area Data Assessment Committee (TA-DAC)

An internal GSK Safety Review Committee (iSRC), independent of the study team, will maintain governance of the study and will periodically review all available data in an un-blinded manner with a focus on key safety parameters. A Therapeutic Area (Immuno-Inflammation) Data Assessment Committee (TA DAC), independent of the study team, will periodically review un-blinded efficacy data and at the interim analysis will advise the iSRC on adaptive design changes should such changes be required. An iSRC charter details the activities of these committees, including when and which data will be reviewed, how the integrity of the study will be maintained, and the membership of both committees.

The overall responsibility of the iSRC is to protect the ethical and safety interests of subjects recruited into the study while also protecting the scientific validity of the data. The iSRC has the primary governance role for the study.

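### Section 9.4.2 lets investigator-assessed relationship to IP lead the reading of a primary safety endpoint whose only named measure is incidence, with no causality qualifier

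*Protocol*

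**What the plan says.** The primary endpoint in Section 3 (repeated in the synopsis) is "Safety and tolerability; including incidence of SAEs and AESIs". Section 7.4.1.4 lists the AESIs as categories of event, without reference to cause, and adds: "The analyses of these events will be described in the Reporting and Analysis Plan".

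Section 9.4.2, on the analysis of the primary endpoints, rules out formal testing, uses the safety population, and rests clinical interpretation on displays of AEs, laboratory values and vital signs. It then sets the priority: "The principle consideration in this evaluation will be the investigator-reported relationships of either AEs or laboratory abnormalities to IP". The section does not mention incidence, SAEs, AESIs or treatment arm.

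Three other places speak of safety events in the co-administration arm without a relatedness condition:

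- Section 9.2.1 gives a flat-prior 95% interval for the probability of a safety event when 1 of 20 subjects has one.
- Section 9.2.2 tabulates upper limits by "Number of particular safety events observed with co-administration".
- Section 5.4.4 has the study stopped if the rate of low IgG "associated with serious infection or fatal infection rate exceeds 20% in the co-administration therapy arm".

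**The concern.** The main safety question is whether giving both drugs adds risk, chiefly of infection. A randomized, placebo-controlled trial answers that most directly by setting event rates side by side by arm, whatever the investigator thought caused each event. Section 9.4.2 gives first place to case-by-case judgements instead. The stated lead therefore does not match the measure named in the endpoint, nor the quantity for which Section 9.2 works out the precision.

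At stake is the emphasis of the safety conclusion. A reader following 9.4.2 literally could give less weight to an excess of infections in the co-administration arm if most had been judged unrelated one at a time.

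**Working it through.** **1. The plan's own figures.** Inputs from Section 9.2.1: Beta(1,1) prior, 1 event in 20, posterior Beta(2,20). Its 2.5% and 97.5% quantiles are 0.0117 and 0.2382, which match the printed 0.01 to 0.24. The six upper limits in Section 9.2.2 follow from the same method, as the 97.5% quantile of Beta(x+1, n−x+1):

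| Events / n | Computed | Printed |
|---|---|---|
| 0/18 | 17.6% | 18% |
| 1/18 | 26.0% | 26% |
| 0/16 | 19.5% | 20% |
| 1/16 | 28.7% | 29% |
| 0/14 | 21.8% | 22% |
| 1/14 | 31.9% | 32% |

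The figures hold. They describe the probability of a safety event, with no filter for cause.

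**2. Where relatedness is used.**

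| Place | Purpose | Relatedness condition |
|---|---|---|
| 1 and 3 | Primary endpoint | None |
| 7.4.1.4 | AESI categories | None |
| 9.2.1, 9.2.2 | Precision for the primary endpoint | None |
| 5.4.4 | Study stopping rule | None |
| 5.4.1 | Dose delay or withholding | Yes |
| 5.4.3 | Discontinuation for severe skin reactions | Yes |
| 4.3.2, 7.1 footnote 18, 7.4.1.1 | SAE collection in individualized follow-up | Yes, except fatal SAEs and designated AESIs |
| 9.4.2 | Interpretation of the primary endpoint | Yes, as the leading consideration |

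Relatedness does appear elsewhere in the protocol, but those uses concern management of individual subjects or the scope of late data collection. None concerns the primary analysis, and no current section reconciles 9.4.2 with the endpoint.

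**3. How much attribution can tell here.**

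- Section 6.3 blinds investigators to arm, so they cannot attribute an event to the combination as such.
- Section 6.3 also blinds them to unblinding laboratory data, with B-cell counts, IgM and IgA given as examples. They cannot report a relationship for abnormalities that they do not see, although 9.4.2 relies on such reports.
- Section 4.7 says there are no clinical trial data on co-administration to inform a judgement.
- Section 4.7.1 treats infections as expected with both drugs, and cites one 5% infection rate in SLE for subjects on belimumab or placebo. Single cases are therefore hard to assign.

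**4. What counting only related events would do (illustration).** Section 9.4.2 does not prescribe such a count. With assumed true incidence p and assumed share s called related, P(no event counted in 20) = (1 − p·s)^20.

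| p | s = 1 | s = 0.5 | s = 0.25 |
|---|---|---|---|
| 0.20 | 1.2% | 12.2% | 35.8% |
| 0.10 | 12.2% | 35.8% | 60.3% |

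The documents give neither p nor s. The table shows only that such a count would be sensitive to s.

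**5. Precision of the alternative.** For an assumed 4/20 against 1/10, the Wilson limits are 0.081 to 0.416 and 0.018 to 0.404. The Newcombe 95% interval for the difference of 10 points has lower limit 0.10 − √[(0.200 − 0.081)² + (0.404 − 0.100)²] = −0.227 and upper limit 0.10 + √[(0.416 − 0.200)² + (0.100 − 0.018)²] = +0.331. By-arm incidence is imprecise at this size.

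**The case against.** The strongest reply is that little follows in practice. Section 9.4.2 displays all AEs, not only related ones. There is no formal safety comparison to distort (Section 9.1). The iSRC "will periodically review all available data in an un-blinded manner with a focus on key safety parameters", and Section 7.4.1.4 leaves the AESI analyses to the RAP. The endpoint is safety and tolerability, of which incidence is only an included part, so 9.4.2 redefines nothing. All of this stands, and it is why the point is minor. Deferral to the RAP does not remove it: the protocol itself fixes which consideration leads, and a RAP that led with all-causality incidence would contradict it.

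Nor is it shown that attribution is always less sensitive. Assume incidences of 10% on placebo (n = 10) and 20% on co-administration (n = 20). The chance that the observed co-administration rate is the higher is 73% counting all events. Counting related events only, it is 63% if half of all events are called related regardless of cause (10% against 5%). It is 77% if 80% of drug-caused and 20% of background events are called related (0.8 × 10% + 0.2 × 10% = 10% against 0.2 × 10% = 2%). The direction depends on how well investigators discriminate. Blinding and overlap with expected infections make good discrimination doubtful here, but that is a judgement, not a demonstration.

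A reader might go further and infer that events judged unrelated drop out of the primary evaluation, so that the zero-count chances above measure a real loss. The documents do not support that: 9.4.2 orders considerations and does not restrict what is counted. A reader might also infer that every other safety rule ignores cause; Sections 4.3.2, 5.4.1, 5.4.3 and 7.4.1.1 show otherwise.

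**Conclusion.** The mismatch is real and in current text, and it is a stated rule rather than a missing detail. It concerns only which quantity leads the interpretation of the primary safety objective. No data, display or iSRC review is affected, and no printed figure changes. Its effect on the conclusions cannot be quantified from the documents. The judgement that attribution is a poor lead rests on the protocol's own blinding rules, on the absence of trial data for the combination, and on infections being expected with both drugs. Minor; a cheap improvement.

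**What to change.** Replace the sentence in Section 9.4.2 with: *The principal consideration will be the all-causality incidence of SAEs, AESIs and laboratory abnormalities by treatment arm, presented descriptively with no formal comparison (Section 9.1); investigator-assessed relationship to IP is supportive.*

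This needs no new data, test or sample size, and touches no dosing or clinical-management rule. Descriptive between-arm intervals are optional and can be left to the RAP. The cost is one sentence. The drawback is the imprecision of by-arm incidence, which is the reason to keep relatedness as supportive information and not drop it.
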